4.1 Interim Analysis

No interim analyses are planned for this study.

4.2 Analysis Populations

Inclusion and exclusion from each analysis population will be decided at the Blind Data Review Meeting (BDRM) prior to database lock. Further exclusions may be made from PK and PD populations based on the plasma concentration data.

Randomized Population

The randomized population consists of all enrolled subjects who sign the informed consent form (ICF), and randomised in the study, regardless of whether subjects received a dose of study drug. Subjects who prematurely withdraw from the study for any reason and for whom an assessment is not performed will still be included in the randomized population. Subjects will be summarized according to their randomized treatment group.

Safety Population

The safety population will consist of all subjects who receive at least 1 dose of the study drug.

PK Population

The PK population will consist of all subjects who have sufficient plasma samples data to enable the calculation of at least one of the following PK parameters: C_{max} , AUC_t or AUC_{∞} for plasma total Mo under both treatments, A and B. Subjects who did not receive the full dose of study drug will be excluded from the PK population.

PD Population

The PD population will consist of all subjects who have sufficient plasma samples which will enable the evaluation of the PD effects, that is for whom at least one absolute and percentage change of plasma copper levels in terms of either Cu, Cp, CpC or NCC is available under both treatments, A and B.

4.3 Subject Disposition

All subjects enrolled will be included in the summary of subject disposition. This will present the overall number of subjects screened and by treatment sequence and overall the frequency and percentage of subjects randomized and treated, and who completed or discontinued from the study, along with reason for discontinuation. Furthermore, the number and percentage of subjects in each analysis population will be tabulated. Discontinued subjects will be listed. Subject assignment to analysis populations will be listed. Screen Failures will not be listed or included in summary tables.

4.4 Demographic Characteristics

Individual subject demographics (including age, sex, race and ethnicity), body measurement data (height, body weight and body mass index) at screening and menstruation information (regular cycle, first day of last cycle, average cycle length) will be listed and summarized (excluding menstruation information) by each treatment sequence and overall for the safety population. If the remaining analysis populations are different from the safety population by more than 5%, separate demographic tables will be produced. Height will be measured in centimetres and weight in kilograms. Body mass index will be given in kg/m².

4.5 Baseline and Other Safety Characteristics

Data collected from virus serology, serum pregnancy test, alcohol breath test and urine drug screen will be listed by subject.

4.6 Inclusion and Exclusion Criteria

The inclusion and exclusion criteria will be listed together with the overall eligibility for each subject and the frequency of failed inclusion or exclusion criteria will be summarized.

4.7 Protocol Deviations

The final review of protocol deviations will be performed prior to database lock. The protocol deviations will be listed and summarized by treatment sequence.

4.8 Medical History

Medical history data will be coded using the Medical Dictionary for Regulatory Activities (MedDRA) dictionary Version 21.0 (or higher). Medical and surgical history data will be listed individually and summarized by treatment sequence.

4.9 Study Drug Administration and Meals

As per protocol, study drug dosing will occur with the subject being in a fasted state.

Study drug administration data will be listed individually.

Meal (breakfast, lunch, dinner, snacks) times and consumption grade will be listed.

4.10 Prior and Concomitant Medications

All prior and concomitant medications will be coded using the World Health Organization Drug Dictionary version June 1, 2018 or higher and will be listed individually.

Prior medications are defined as those for which the end date and time is prior to the date, and time of first study drug administration.

Concomitant medications are defined as those either with start date and time on or after the date and time of first study drug administration, or those with start date and time prior to the first study drug administration and continuing at the time of first dose of study drug administration.

If medication/therapy dates or times are incomplete and it is not clear whether the medication/therapy was concomitant, it will be assumed to be concomitant.

All prior and concomitant medications/therapies will be listed by subject using reported name, anatomical therapeutic chemical (ATC) Term and World Health Organization drug dictionary (WHO-DD) Preferred Name, indication, dose, dose unit, frequency, route of administration, start date and end date or 'ongoing' flag and duration of use. Concomitant medications will be flagged.

The number and percentage of subjects with concomitant medication/therapy will be summarised overall and by WHO-DD Preferred Name and ATC Term using the safety population. Prior medication will be summarized in the same way as concomitant medication.

Non-pharmacologic therapies and procedures will be listed separately.

4.11 Safety Analyses

All safety analyses will be performed on the safety population.

Safety analyses will include an analysis of all AEs, ECGs, clinical laboratory data, physical examinations, and vital sign measurements using descriptive statistics. No inferential statistical analyses are planned on the safety parameters of this study.

4.11.1 Adverse Events

A Treatment Emergent Adverse Event (TEAE) is any adverse event that commences after the start of administration of study drug. TEAEs will further be classified by the Period in which they commenced. A TEAE will be classified as Period 1 if the AE start date/time is on or after the date and time of drug administration in Period 1, and Period 2 if the AE start date/time is on or after the date and time of drug administration in Period 2.

The incidence of TEAEs (after dosing) will be summarized using the safety population.

The MedDRA dictionary Version 21.0 (or higher) will be used to classify all AEs reported during the study by System Organ Class (SOC) and Preferred Term.

A summary of TEAEs including the incidence of subjects who experienced TEAEs (number and percentage of subjects) and incidence of TEAEs (number of events) will be presented for each period, treatment and overall, by toxicity and by relationship to study drug.

TEAEs and serious TEAEs will be summarized by SOC and Preferred Term for each period and treatment and overall, and by relationship to study drug and by toxicity.

Subjects having multiple AEs within a category (e.g., overall, SOC and Preferred Term) will be counted once in that category.

For toxicity tables, a subject's worst toxicity event within a category will be counted. For relationship tables, a subject's event with greatest relationship to study drug within a category will be counted.

In each table, SOC and Preferred Term will be presented in descending order of overall incidence rate (alphabetical order will be used in case of equal rates).

All adverse events will be listed. Serious TEAEs and AEs resulting in withdrawal from the study will be listed separately.

Adverse events during screening will be summarized by treatment sequence and overall.

4.11.2 Laboratory Data

Clinical laboratory parameters (including blood chemistry, haematology, coagulation, urinalysis and other laboratory results) will be listed and abnormal parameters will be flagged as high (H) or low (L) according to reference ranges. Absolute (observed) values and changes from baseline (continuous variables) will be summarized for each parameter and scheduled time point by treatment. The last lab value will be used for summary analysis if repeated measurements are made at any time point.

For summary statistics, a lab value with "<" will be replaced with a numeric value by removing the "<" sign. In the listings, the values will be displayed as originally reported by the laboratory.

Laboratory parameter values will be graded according to the Common Terminology Criteria for Adverse Events (CTCAE) and summarized by CTCAE grade. Non-protocol parameters will only be listed, in a separate listing, if required. Shift tables by treatment will be produced for all other laboratory parameters. These tables will summarize the number of subjects with each baseline grade relative to the normal ranges and changes to the worst highest grade assessed post-dose during the study. Similarly, shift tables from baseline based on NCI toxicity grade will be created.

As per the study protocol, any laboratory tests with values considered clinically significantly abnormal are to be repeated until the values return to normal or baseline or are no longer considered clinically significant by the Investigator or medical monitor. For all summary analyses, only the last available of all repeated measurements is to be used.

4.11.3 Electrocardiograms

ECG parameters will be measured at the time points specified in the study protocol and will at least include heart rate, PR interval, RR interval, QRS duration, interval between the start of the Q wave and the end of the T wave in an ECG (QT), and corrected QT interval corrected using Fridericia's formula (QTcF), where QTcF=QT/RR^1/3. The variables will be listed individually.

Three or more replicate measurements are taken at each protocol time point and the arithmetic mean of the evaluable/available measurements will be taken as the measurement to be used for summary statistics. Arithmetic mean values will also be included into the listings.

For ECG variables, the change from baseline will be derived using the arithmetic mean value of each time-point triplicate minus the arithmetic mean of baseline triplicate values per period.

Mean absolute (observed) values and corresponding changes from baseline in the ECG variables will be summarized by treatment and time point.

An outlier analysis will be performed on mean values that will summarize the frequency and percentage of subjects who meet any of the following outlier criteria at each visit by treatment:

- QT, QTcF interval > 450 msec to ≤ 480 msec
- QT, QTcF interval > 480 msec to ≤ 500 msec
- QT, QTcF interval > 500 msec

- QT, QTcF interval increases from baseline > 30 msec to ≤ 60 msec
- QT, QTcF interval increases from baseline > 60 msec

As per the clinical study protocol, recorded ECGs will be reviewed by the Investigator, or qualified designee, and abnormal ECGs may be followed by additional safety recordings. For summary analyses, the additional safety ECGs will be used only, and will replace the initial ECGs that were reviewed as abnormal.

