6.6.1.1. General Adverse Reaction rules

The general adverse reaction rules refer to all adverse reactions, excluding those relating to the liver and hematology and QT interval prolongation. The CTCAE may not give clear enough guidance, and grading may not be appropriate for this study in healthy volunteers; therefore, special study-specific rules have been created.

Individual Adverse Reaction Rules

An individual subject will not receive the dose of ALXN1840 in the subsequent period, if either of the following occurs:

• Subject experiences any CTCAE Grade 3 (or higher) adverse reaction, or a serious adverse reaction, irrespective of severity/CTCAE grade.

• Subject experiences any CTCAE Grade 1 or 2 adverse reaction considered to be related to study drug that is considered a safety concern by the Safety Review Committee.

Group Adverse Reaction Rules

Dosing will be suspended for all subjects, or potentially only in an affected cohort, if either of the following occurs:

- One subject (among any of the 48 total subjects) experiences a non-serious, severe (CTCAE Grade 3) adverse reaction.
- One subject experiences a serious adverse reaction, irrespective of severity/CTCAE grade.

In the event of suspension of dosing, continuation of the study will require a protocol amendment that has been approved by the MHRA and ethics committee.

Special individual Adverse Reaction Rules

Dosing in an individual subject will be suspended if they experience any of the following:

- Liver function test elevation
 - ALT or AST value $> 3 \times ULN$ together with bilirubin increase $> 2 \times ULN$.
 - ALT or AST value $> 8 \times ULN$.
 - ALT or AST value $> 3 \times ULN$, and symptomatic.
- Hematology
 - Hemoglobin reduction to an absolute value of 8g/dL (80g/L) or lower.
 - Platelet count reduction of > 50% from baseline or absolute value < 80.000/mm³ (Day -1 blood samples).
- QT interval prolongation
 - A prolongation of the uncorrected QT interval of > 500ms (using consistent, technically valid triplicate ECG).

Special group AR rules

If 1 subject fulfils the special individual adverse reaction rules, and this could be reasonably attributed to study drug, a Safety Review Committee meeting will be arranged and, if necessary, dosing for all subjects will be temporarily suspended until the Safety Review Committee meets. At this meeting, a decision will be made regarding the continuation of dosing in the remaining subjects.

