8.2.3. Electrocardiograms

8.2.3.1. Recording of 12-Lead ECGs

A triplicate 12-lead ECG will be obtained using a GE Marquette MAC1200® / MAC1200ST® recorder connected via a fixed network connection to the MUSE® Cardiology Information System (MUSE) after the subject has been resting for at least 10 minutes. 12-lead ECGs will be conducted before PK/PD/biomarker blood sampling if these 2 events occur at the same time. The timing of 12-lead ECGs is described in the Schedule of Activities (Table 1 and Table 2).

12-lead ECGs recorded during screening will be stored electronically on the MUSE information system. Only ECGs recorded electronically will be valid ECGs for any purpose other than safety assessment. ECG printouts may be filed in the subject's case report form (CRF) for medical safety reviews.

Each 12-lead ECG recorder will be set up to the required technical specifications and containing the information required to identify the records. Each ECG recording will be clearly identified (Subject ID, visit date, and the actual times of ECG recordings).

12-lead ECG recordings will be made after the subjects have been resting in a supine position for at least 10 minutes. The subjects will avoid postural changes during the ECG recordings and clinical staff will ensure that subjects are awake during the ECG recording.

At each time point, the 12-lead ECG will be recorded in triplicate, to reduce variance and improve the precision of measurement. The triplicates will be performed at approximately 1-minute intervals. Each ECG recording (trace) will last 10 seconds. Repeat ECGs will be performed until at least three 10-second ECG records per scheduled time-point meet the quality criteria set out in the Study Operations Manual and the applicable Standard Operating Procedure to enable reading and analyzing at least 5 complexes per derivation.

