8.2.3.2. Safety Review of 12-Lead ECGs

All recorded 12-lead ECGs will be reviewed by the Investigator, or qualified designee, and the review findings will be documented in the CRF. If a subject shows an abnormal ECG, additional safety recordings (including the use of 5- or 12-lead Holter equipment) may be made and the abnormality be followed to resolution, if required.

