Baseline will be defined as the last non-missing value among assessments recorded prior to first administration of study drug per period, where unscheduled assessment at the respective scheduled study are also taken into account. Changes from baseline values will be calculated as the post-baseline assessment value minus the baseline value per period. In general, only observed values from scheduled time points will be used to create summary tables, with the exception of unscheduled assessments on the respective study day. It is assumed that unscheduled assessments on scheduled study days are repetitions of potentially invalid scheduled assessments, and thus those unscheduled assessments will replace the respective scheduled assessments for summary tables and further statistical analyses.

Early Termination (ET) visits will be recoded to ET visits where necessary and reported as ET.

Deviations from the planned analyses will be described in the final clinical study report (CSR).

Page layout of the TFLs will be in landscape mode and will be provided as RTF files in Microsoft Word. Final TFLs will additionally be created in bookmarked portable document format (PDF). Further details of page layout will be provided in the TFL shell document.

All statistical analyses will be conducted using SAS® for Windows® Version 9.3 or higher.

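### SAP 4.11.3 lets a follow-up safety ECG displace an initial ECG read as abnormal, and does not exempt the QT/QTcF outlier table (minor)

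*SAP*

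**What the plan says.** **ECG analysis.** SAP 4.11.3 takes the mean of the replicate ECGs at each time point and plans an outlier analysis on those means. It will "summarize the frequency and percentage of subjects who meet any of the following outlier criteria at each visit by treatment". The absolute rows start above 450 msec and end at "QT, QTcF interval > 500 msec"; two further rows count increases from baseline above 30 and above 60 msec. The section closes with: "For summary analyses, the additional safety ECGs will be used only, and will replace the initial ECGs that were reviewed as abnormal".

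**General rule.** SAP 4 builds summary tables from scheduled values, "with the exception of unscheduled assessments on the respective study day". It assumes that these redo scheduled assessments that may have been invalid, and concludes that "those unscheduled assessments will replace the respective scheduled assessments for summary tables and further statistical analyses".

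**Protocol.** Section 8.2.3.1 deals with recording quality: "Repeat ECGs will be performed until at least three 10-second ECG records per scheduled time-point meet the quality criteria". Section 8.2.3.2 deals with abnormal findings: "additional safety recordings (including the use of 5- or 12-lead Holter equipment) may be made and the abnormality be followed to resolution", if required. Section 6.6.1.1 contains an individual QT rule: "A prolongation of the uncorrected QT interval of > 500ms (using consistent, technically valid triplicate ECG". Section 9.4.2 averages the triplicates at the time points collected and has no replacement step.

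**Laboratory data.** SAP 4.11.2 says that the shift tables show the highest post-dose grade, as protocol 9.4.2 does. It also says that summary analyses use only the last of any repeated measurements.

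**The concern.** An outlier table exists to count extreme readings. A rule that swaps out a reading because it was judged abnormal works against that purpose. It acts in one direction only: normal ECGs are not displaced by later ones under this sentence, abnormal ones are.

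Safety and tolerability is the only secondary objective, and this table is the only planned count of QT/QTcF readings by category. Its top absolute row uses the same 500 msec cut-off as the QT rule in protocol 6.6.1.1, so a triplicate that met that rule could be absent from the matching SAP row. The rule itself is not questioned here.

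The laboratory section raises a smaller question of the same kind: it states a worst-grade rule and a last-repeat rule without saying which governs the shift and CTCAE-grade tables.

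**Working it through.** The plan gives no figure on this point to reproduce. The check is a comparison of texts, with simple counts.

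**1. Does the replacement rule reach the outlier table?** SAP 4.11.3 speaks of summary statistics for the triplicate means, and SAP 4.11.4 does so for repeated vital signs. The ECG replacement sentence uses the wider term summary analyses. The outlier analysis is itself described as one that summarizes subjects, and SAP 4 extends replacement to tables and further analyses. No sentence exempts the outlier table, so as written the rule reaches it.

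**2. Is the displaced ECG an invalid one?**

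| Situation | Where handled | Trigger |
|---|---|---|
| Poor trace | Protocol 8.2.3.1 | Quality criteria not met; repeated until three traces pass |
| Abnormal finding | Protocol 8.2.3.2 | Investigator's review; extra recordings optional |
| Replacement in summaries | SAP 4.11.3 | Initial ECG reviewed as abnormal |

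The SAP trigger matches the second line, not the first. The invalidity assumption in SAP 4 therefore does not describe these recordings.

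**3. When does a count change?** All of the following must hold: the initial triplicate passed the quality criteria and is outlying; it was reviewed as abnormal; an additional recording was made; and the additional value is low enough to cross a row boundary. A numeric outlier not reviewed as abnormal stays in, as does a repeat that is still in the same band.

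**4. Hypothetical subject** (values assumed for illustration): baseline 420, initial triplicate mean 485, additional recording 430 msec.

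- Initial value: 485 − 420 = +65. The subject counts in the > 480 to ≤ 500 row and in the increase > 60 row.
- After replacement: 430 − 420 = +10. The subject counts in no row.
- An additional value above 450 and up to 480 would instead move the subject to the lowest absolute band.

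**5. Size per subject.** With 48 enrolled, 1/48 = 2.08%; with the minimum of 40 completers, 1/40 = 2.50%. In a rare row such as > 500 msec, one displacement turns 1 of 48 into 0 of 48.

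**6. Readings within reach.** Protocol Table 2 schedules post-dose ECGs at 4, 24 and 96 h: 3 × 40 = 120 to 3 × 48 = 144 triplicates per treatment, plus the end-of-study ECG. These are readings to which the rule could apply, not expected losses. The documents give no rate of abnormal or repeated ECGs.

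**7. Same-study-day limit.** SAP 4 admits unscheduled values only on the respective study day; SAP 4.11.3 does not say whether that limit applies. If it does, the problem narrows but remains: a later Day 1 recording could still displace the 4-hour ECG.

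**8. Laboratory data.** Take hypothetical grades 0, 0, 2 and 0 at four draws, with the grade 2 repeated as grade 0.

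- Last-repeat rule: max(0, 0, 0, 0) = 0.
- Worst-assessed rule: max(0, 0, 2, 0, 0) = 2.

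The rules differ only when the worst value was itself repeated with a lower grade. Scheduled post-dose draws per treatment, besides end of study:

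- Hematology and chemistry: 4 (4, 24, 96 and 216 h), so 4 × 40 = 160 to 4 × 48 = 192.
- Urinalysis and coagulation: 3, since neither is sampled on Day 10, so 3 × 40 = 120 to 3 × 48 = 144.

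**The case against.** **The SAP gives a reason for replacement.** It assumes that unscheduled assessments redo possibly invalid ones. The protocol's quality criteria sit in an operations manual and a procedure that the documents do not reproduce, so passing them does not prove a trace free of every error. That caution stands. It does not rescue the rule, because the ECG sentence turns on abnormality and protocol 8.2.3.2 describes clinical follow-up.

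**Nothing is lost from the record.** ECG values are listed by subject, clinically significant findings meet the adverse event definition, and a QT above 500 msec would lead to action under protocol 6.6.1.1. The effect also needs a discretionary re-recording, the analysis is descriptive, and both earlier 60 mg healthy-subject studies reported no clinically important ECG trends (protocol 2.2). All of this stands and is why the point is minor. Listings and event tables still do not replace a count by QT category.

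**Using only the initial triplicates would be no better.** It would drop a follow-up ECG that is longer than the scheduled one. This is right, and the fix has to use both.

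**The laboratory text has a natural reading.** The worst-grade sentence is specific to the shift tables and agrees with protocol 9.4.2, so it would ordinarily prevail over a general repeat rule. A reader might infer that SAP 4.11.2 removes the worst laboratory values from the shift tables; the documents do not support that. What remains is an ambiguity worth one sentence.

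**Conclusion.** The ECG point holds: as written, SAP 4.11.3 can remove a quality-passed outlying triplicate from its row of the QT/QTcF table, or move it to a lower band. Each such subject changes a cell by 2.1 to 2.5 percentage points. This rests on reading summary analyses to include the outlier table, which the wording favors and no text contradicts.

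A reader might go further and infer that the plan will conceal a QT signal, or that a particular share of outliers will be lost. The documents support neither: they give no QTcF distribution, rate of abnormal reviews or re-recording rate, and the values stay in the listings. Nor is the dosing rule in protocol 6.6.1.1 weakened, since the SAP sentence concerns summaries only. The same change is not needed for vital signs, because SAP 4.11.4 plans no outlier table.

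Severity is minor. The primary bioavailability analysis is untouched, and the laboratory part is a clarification only.

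**What to change.** **SAP 4.11.3.** Build the QT/QTcF outlier table from all post-dose triplicate means that met the protocol quality criteria, both the initial scheduled triplicates and any additional safety triplicates. Count each subject at the worst value per visit and treatment. State that follow-up ECGs do not replace initial ones in this table, and limit replacement to technically invalid recordings. State how an additional recording is assigned to a visit, including whether the same-study-day limit of SAP 4 applies.

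**SAP 4.11.2 (secondary).** State that the worst-grade rule, as in protocol 9.4.2, governs the shift and CTCAE-grade tables, taken over all valid values after the dose of the treatment concerned. Confine the last-repeat rule to time-point summary statistics. Exclude samples with documented technical issues.

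**Cost.** SAP wording and minor programming, with no new visits or assessments. The documents do not show that additional ECGs are taken in triplicate or that a reason for each laboratory repeat is recorded. The SAP should therefore say that only additional ECGs recorded as triplicates that meet the quality criteria are used, and that a laboratory value with no documented technical issue counts as valid. The downside is that a few isolated, unconfirmed abnormal values will appear in the tables.
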